9.4 Analysis of the primary variable

9.4.1 Variable

The primary efficacy variable is a binary composite endpoint of tBPAR or eGFR (MDRD4) < 50 mL/min/1.73m² at Month 12 post-transplantation. The component of eGFR (MDRD4) < 50 mL/min/1.73m² at Month 12 is defined as an incidence of eGFR (MDRD4) < 50 mL/min/1.73m² in the Month 12 visit window.

9.4.2 Statistical model, hypothesis, and method of analysis

The primary analysis will be performed on the Full Analysis Set following the intent-to-treat principle. The proportion of subjects meeting the primary endpoint of tBPAR or eGFR (MDRD4) $< 50 \text{ mL/min/}1.73\text{m}^2$ at Month 12 will be compared using a confidence interval approach.

Treatment by CNI interaction for the composite endpoint of tBPAR or eGFR (MDRD4) < 50 mL/min/1.73m² will be assessed using a logistic regression model (see Section 9.4.4 for risk factor analysis). If the interaction is not significant at the level of 0.10, i.e. the effects of treatment are similar for each CNI, then the primary analysis will be based on the pooled CNIs, i.e. everolimus plus reduced CNI (EVR+rCNI) vs. MPA plus standard CNI (MPA+sCNI). If this test shows significantly different event rates for tacrolimus vs. cyclosporine, then testing will be performed for the 2 CNIs separately, with the tacrolimus subgroup being considered primary

Event rates will be compared between groups using the following hierarchical testing strategy:

- a) Non-inferiority of EVR+rCNI vs. MPA+sCNI will be evaluated based on the primary endpoint of tBPAR or eGFR (MDRD4) < 50 mL/min/1.73m² at Month 12 using a 10% non-inferiority margin (see Section 9.4.2.1).
- b) Non-inferiority of EVR+rCNI vs. MPA+sCNI will be evaluated with a 10% noninferiority margin for the key secondary endpoint of tBPAR, graft loss or death at Month 12 (see Section 9.5.1).
- c) Superiority of EVR+rCNI to MPA+sCNI will be evaluated based on the primary endpoint of tBPAR or eGFR (MDRD4) < 50 mL/min/1.73m² at Month 12 (see Section 9.4.2.2).

The above hierarchical fixed hypothesis testing procedure will not inflate overall Type I error rate. Therefore, each hypothesis will be tested at the one-sided 0.025 significance level and no multiplicity adjustment is needed.

Non-inferiority of everolimus plus reduced CNI to MPA plus standard 9.4.2.1 CNI

The null hypothesis:

 H_{01} : $R_{EVR+rCNI}$ - $R_{MPA+sCNI} \ge 0.10$ (non-inferiority margin): the difference in proportion of subjects experiencing tBPAR or eGFR (MDRD4) < 50 mL/min/1.73m² at 12 months between the everolimus plus reduced CNI (R_{EVR+rCNI}) and the MPA plus standard CNI arm (R_{MPA+sCNI}) is at least 10%.

The alternative hypothesis:

 H_{A1} : $R_{EVR+rCNI}$ - $R_{MPA+sCNI}$ < 0.10 (non-inferiority margin): The difference in proportion of subjects experiencing tBPAR or eGFR (MDRD4) < 50 mL/min/1.73m² at 12 months between the everolimus plus reduced CNI (R_{EVR+rCNI}) and the MPA plus standard CNI arm (R_{MPA+sCNI}) is less than 10%.

9.4.2.2 Superiority of everolimus plus reduced CNI to MPA plus standard CNI The null hypothesis:

 H_{03} : $R_{EVR+rCNI}$ - $R_{MPA+sCNI} \ge 0$: the proportion of subjects experiencing tBPAR or eGFR $(MDRD4) < 50 \text{ mL/min}/1.73\text{m}^2$ at 12 months in the everolimus plus reduced CNI $(R_{EVR+rCNI})$ arm is greater than or equal to that in the MPA plus standard CNI arm (R_{MPA+sCNI}) arm.

The alternative hypothesis:

H_{A3}: R_{EVR+rCNI} - R_{MPA+sCNI} < 0: the proportion of subjects experiencing tBPAR or eGFR $(MDRD4) < 50 \text{ mL/min}/1.73\text{m}^2$ at 12 months in the everolimus plus reduced CNI $(R_{EVR+rCNI})$ arm is less than that in the MPA plus standard CNI arm (R_{MPA+sCNI}) arm.

Both hypotheses H_{01} and H_{03} will be tested at the significance level of $\alpha = 0.025$ (one-sided). A Z-test based 95% confidence interval will be constructed for the difference in proportion of subjects experiencing tBPAR or eGFR (MDRD4) < 50 mL/min/1.73m² at 12 months between the everolimus plus reduced CNI arm (R_{EVR+rCNI}) and the MPA plus standard CNI arm (R_{MPA+sCNI}). The everolimus plus reduced CNI arm will be claimed to have a non-inferior incidence of tBPAR or eGFR (MDRD4) < 50 mL/min/1.73m² compared to the MPA plus standard CNI arm if the upper limit of the 95% CI is below 10%. The everolimus plus reduced CNI arm will be claimed to be superior to the MPA plus standard CNI arm with respect to composite endpoint of tBPAR or eGFR (MDRD4) < 50 mL/min/1.73 m² at 12 months if the upper limit of the 95% CI is less than 0.

However, following the aforementioned hierarchical fixed hypothesis testing procedure, the hypothesis H₀₃ for superiority of EVR plus reduced CNI to MPA plus standard CNI will be evaluated if non-inferiority of EVR plus reduced CNI vs. MPA plus standard CNI is achieved for the primary endpoint (rejecting the hypothesis H₀₁) and the key secondary endpoint of tBPAR, graft loss or death at Month 12 (rejecting the hypothesis H₀₂, see Section 9.5.1).

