5.3 Treatment assignment, randomization

At the Baseline Visit, within 24 hr of completion of transplant surgery, all eligible subjects will be randomized via Interactive Response Technology (IRT) to one of the treatment arms. Randomization will be stratified, within the treatment groups, by donor type (living donors (LD), deceased standard criteria donors (SCD) and deceased expanded criteria donors (ECD)) and CNI usage, cyclosporine vs tacrolimus. The investigator or his/her delegate will contact the IRT after confirming that the subject fulfills all the inclusion/exclusion criteria. The IRT will assign the subject to a treatment arm and will specify the treatment to be dispensed to the subject. The randomization number will not be communicated to the caller. For subjects who are not eligible to be randomized post-transplantation the IRT must be informed that the subject is a screen failure and the screen failure recorded on the Screening disposition CRF.

The randomization numbers will be generated using the following procedure to ensure that treatment assignment is unbiased and concealed from subjects and investigator staff. A subject randomization list will be produced by the IRT provider using a validated system that automates

the random assignment of subject numbers to randomization numbers. These randomization numbers are linked to the different treatment arms.

The randomization scheme for subjects will be reviewed and approved by a member of the IIS Randomization Group.

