6.2 Subject demographics/other baseline characteristics

After informed consent has been signed and the subject's eligibility to participate in the study has been determined, baseline subject information will be obtained in accordance with local regulations, including date of birth, age, sex (with child bearing status for females), race and ethnicity. In addition, relevant medical history (including CKD and ESRD history) and current medical conditions at screening, a full physical examination, vital signs and a pregnancy test (for females of child-bearing potential) will also be performed.

At Baseline/Transplantation information on the renal transplant procedure, recipient and donor transplant background, recipient and donor viral serology and recipient/donor HLA testing results will be recorded. Post-transplant, when all Inclusion/Exclusion criteria are met, the subject may be randomized. For randomization of subjects the IRT must be contacted, CNI and Donor status provided and the IRT will assign the treatment group. For all subjects regardless of randomization status the IRT and Screening Disposition CRF must be completed to

Protocol No. CRAD001A2433

document all consented subjects as either randomized or as screen failures and the reason for screen failure recorded in the CRF.

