9.4.3 Handling of missing values/censoring/discontinuations

Since the subjects who have prematurely discontinued study regimen are followed on standard of care, renal function data (e.g. creatinine) and kidney allograft biopsy data will be collected post discontinuation of study regimen for these visits, it is expected that few subjects would be missing efficacy and/or renal function evaluation for the 12 month analysis.

To define the primary variable – composite endpoint of tBPAR or eGFR (MDRD4) < 50 mL/min/1.73m², the following imputation method will be applied for subjects with missing 12month eGFR value. As allograft biopsy data will be collected on an as needed basis due to the nature of kidney transplant studies, no particular rule for missing biopsy will be applied.

- Under the assumption of missing not at random (MNAR), subjects who lost their grafts will be assigned a value of zero for their 12-month eGFR;
- Otherwise, under the assumption of missing at random (MAR), subjects who had missing values including those who died with a functioning graft will have a 12-month eGFR imputed using multiple imputation method based on the longitudinal eGFR (MDRD4) data at all available time points and covariates of randomization strata (donor type and CNI), HLA mismatches ($\leq 3 \text{ vs} > 3$) and induction.

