## 2.2 Analysis Sets

The **full analysis set** (FAS) consists of all randomized and transplanted patients. Patients randomized but not transplanted will be excluded from the FAS. Patients who are mis-randomized due to documented (IVRS) administrative error (eligibility criteria) and have no study drug received are excluded from the FAS. Following the intention-to-treat (ITT) principle, patients will be analyzed according to their randomized treatment assignment and according to the actual stratum they initially belong to.

The **compliance set** (CS) consists of all patients in the FAS who are compliant for both CNI and investigational drug (EVR/MPA). Compliance is defined in [Section 2.4.2](#).

The **per-protocol set** (PPS) consists of all patients in the FAS who complete the study without any major deviations from protocol procedures. Major deviations include:

- Patient received multiple solid organ or tissue transplants (PD ID: EXCL04)
- Renal cold ischemia time > 30 hr (PD ID: INCL04)
- Patient received kidney from a non-heart beating donor (PD ID: INCL06)
- Patient Stratified incorrectly (PD ID: TRT08)
- Patient randomized but did not receive study drug (EVR or MPA) (PD ID: TRT01)
- Patient received treatment other than what they were randomized to (PD ID: TRT07)
- Induction agent other than basiliximab or rATG used (PD ID: TRT05)
- Patient did not receive any basiliximab or rATG for induction use (PD ID: TRT06)
- Prohibited Concomitant Medication used (PD ID: COMD03)
- Prednisone or equivalent was not used during the study (PD ID: TRT14)

The **safety set (SAF)** consists of all patients who received at least one dose of study drug. Patients will be analyzed according to their actual treatment regimen and according to the actual stratum they initially belong to. All safety analyses will be performed on the SAF.

Patients who did not sign the study main informed consent form will be excluded from any analysis sets (FAS, PPS, CS, and SAF). If a patient was mis-randomized due to documented (IVRS) administrative error (eligibility criteria), but received study drug, this patient will belong to both FAS and SAF. [Table 2-1](#) illustrates the selection of patients for the FAS and SAF.

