### 2.2.1 Subgroup of Interest

The following demographic/baseline characteristics are defined at the study level as subgroups for specified analyses:

- Recipient characteristics:
  - Age group: <60 vs ≥60 yr
  - Gender
  - Race: Caucasian, Black, Asian and All other races
  - Region: US, EU, Asia, Australia, Latin America, and Middle East

- DGF (delayed graft function)
- BMI <30 and  $\geq 30$
- Donor/transplant characteristics:
  - Age group: <60 vs  $\geq 60$  yr
  - Gender
  - Cold ischemia time: < 20 vs  $\geq 20$  hr
  - End stage disease leading to transplant (Glomerular disease, Diabetes mellitus and All other diseases)
  - Donor type (living donor, standard criteria and expanded criteria deceased donor): donor type will be derived based on Kidney Donor Background Information eCRF, and not the randomization stratification from IRT.
  - HLA mismatches:  $\leq 3$  vs  $> 3$
- CNI (tacrolimus vs. cyclosporine)
- Induction (basiliximab vs. rATG):
  - Basiliximab: preferred term: BASILIXIMAB; drug code/ID: 10892631
  - rATG: preferred term: ANTITHYMOCYTE IMMUNOGLOBULIN, or ANTITHYMOCYTE IMMUNOGLOBULIN (RABBIT); drug code/ID: 10878131 or 10878151

As early use of rATG can be for delayed graft function, type of induction will be identified as the first intake of rATG or basiliximab by Day 1 post-transplant.

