#### The alternative hypothesis:

$H_{A1}$ :  $R_{\text{EVR+rCNI}} - R_{\text{MPA+sCNI}} < 0.10$  (non-inferiority margin): The difference in proportion of patients experiencing tBPAR or eGFR (MDRD4)  $< 50 \text{ mL/min/1.73m}^2$  at 12 months between the everolimus plus reduced CNI ( $R_{\text{EVR+rCNI}}$ ) and the MPA plus standard CNI arm ( $R_{\text{MPA+sCNI}}$ ) is less than 10%.

The proportion of patients meeting the primary endpoint of tBPAR or eGFR (MDRD4)  $< 50 \text{ mL/min/1.73m}^2$  at Month 12 will be compared using a confidence interval approach.

Multiple imputation will be used as the primary method for handling missing data (see [Section 2.5.3](#) and [Section 4.2.1.1](#) for detail). The analysis first creates multiple (100) imputations of missing eGFR (MDRD4) values under a missing at random (MAR) assumption, resulting in multiple (100) imputed datasets. The imputation model assumes a multivariate normal model for the eGFR (MDRD4) measurements. This model will be estimated separately within each treatment stratum. Together with the tBPAR data, the binary composite endpoint of tBPAR or eGFR (MDRD4)  $< 50 \text{ mL/min/1.73m}^2$  at Month 12 post-transplantation will be derived.

To the resulting 100 imputed datasets, the proportion of patients meeting the primary endpoint of tBPAR or eGFR (MDRD4)  $< 50 \text{ mL/min/1.73m}^2$  at Month 12 will be estimated, yielding 100 sets of parameter estimates and associated covariance matrices. The analysis results are then combined according to Rubin's rules to derive overall estimates and confidence intervals that adequately reflect missing data uncertainty as well as associated p-values (see [Section 4.7.1](#) for sample analysis codes). The everolimus plus reduced CNI arm will be claimed to have a

non-inferior incidence of tBPAR or eGFR (MDRD4)  $< 50$  mL/min/1.73m^2 compared to the MPA plus standard CNI arm if the upper limit of the 95% CI is below 10%.

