### 4.7 Statistical Models

#### 4.7.1 Dummy Codes for Estimating Event Rate, Event Rate Difference and Respective 95% CI as Well as No-Difference Testing for The Composite Endpoint of tBPAR or eGFR < 50 mL/min/1.73m^2

As described in [Section 4.2.1](#), multiple imputation, and control-based imputation will be applied to the primary and sensitivity analyses for the composite endpoint of tBPAR or eGFR < 50 mL/min/1.73m^2. For the component of eGFR < 50 mL/min/1.73m^2, a value for missing eGFR as a continuous variable will be imputed first, then dichotomized it to derive this endpoint.

To estimate event rate, event rate difference and respective 95% CI as well as no-difference testing for tBPAR or eGFR < 50 mL/min/1.73m^2, the following dummy SAS codes can be adapted:

```

*** Use multiple imputation, or control-based imputation method to impute a value for
missing eGFR as a continuous variable;
*** Dichotomized imputed eGFR to derive the endpoint of eGFR < 50 mL/min/1.73m2;
*** Derive the composite endpoint of tBPAR or eGFR < 50 mL/min/1.73m2;
*** Assume the dataset imp_data contains the variable EVENT (event=1 if composite
endpoint of tBPAR or eGFR < 50 mL/min/1.73m2 occurred; =0 otherwise) for each of
of the imputations;

```

```

PROC sort data=imp_data;
  by _imputation_;

```

```
run;

ods output RiskDiffCol2=diff;
proc freq data=imp_data;
  by _imputation_;
  tables trt*event/riskdiff;
run;

*** diff dataset contains the following:

Obs    _Imputation_    Row          Risk          ASE
-----
1       1                Row 1         0.3623        0.0289
2       1                Row 2         0.4729        0.0300
3       1                Total         0.4177        0.0210
4       1                Difference    -0.1106       0.0417
5       2                Row 1         0.3732        0.0291
6       2                Row 2         0.4874        0.0300
7       2                Total         0.4304        0.0211
8       2                Difference    -0.1142       0.0418
... ..

*** Event rate and 95% CI in Treatment1;
proc mianalyze data=diff(where=(row='Row 1'));
  modeleffects risk;
  stderr ASE;
run;

*** Event rate and 95% CI in Treatment2;
proc mianalyze data=diff(where=(row='Row 2'));
  modeleffects risk;
  stderr ASE;
run;

*** Difference in event rate and 95% CI for 'Treatment1 -
Treatment2';
*** P-value for the no-difference test;
proc mianalyze data=diff(where=(row='Difference'));
  modeleffects risk;

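### The primary risk difference and its CI ignore the randomisation strata (donor type, CNI); the test is valid but conservative if event rates differ by stratum, and superiority power is left unused

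*Protocol*

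**What the plan says.** Protocol 5.3 states "Randomization will be stratified, within the treatment groups, by donor type" (living, deceased standard criteria, deceased expanded criteria) and by CNI (cyclosporine or tacrolimus). That makes six strata, with 1:1 allocation. The strata are supplied before assignment: Protocol 6.2 has "CNI and Donor status provided and the IRT will assign the treatment group".

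For the primary endpoint, Protocol 9.4.2.2 says "A Z-test based 95% confidence interval will be constructed for the difference in proportion of" subjects with the composite event. SAP 2.5.2.1 applies this to each imputed dataset, "yielding 100 sets of parameter estimates and associated covariance matrices", and combines by Rubin's rules. The code in SAP 4.7.1 is "tables trt*event/riskdiff", run by imputation, with no stratum variable. Non-inferiority needs the upper limit of this interval below 10%; superiority needs it below 0.

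Donor type and CNI are used elsewhere for the same endpoint: in the imputation model (Protocol 9.4.3, SAP 4.2.1.1), in the logistic model for the treatment-by-CNI interaction (SAP 2.5.2) and as subgroups (SAP 2.2.1). The supportive analyses in SAP 2.5.4 change the analysis set, the subgroup or the imputation. None gives a stratified overall difference.

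**The concern.** Stratified randomisation balances the arms within each stratum, so differences in risk between strata do not contribute to the sampling error of the treatment difference. The crude SE, computed from the overall proportions, still includes them. If strata differ in risk, the interval is too wide, the real one-sided error falls below 0.025 and some power is lost. If they do not differ, nothing changes.

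The documents give reason to expect a difference by donor type. Protocol 4.1 defines expanded criteria donors by age, hypertension, terminal creatinine and cerebrovascular death. Protocol 1.1 lists donor age among the factors implicated in chronic allograft nephropathy. One of the two endpoint components is a low eGFR.

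What is at stake is superiority. Adequate superiority power, overall and in the tacrolimus population, is a stated sample-size goal (Protocol 9.7), and these are the weaker figures in Table 9-1: in the FAS, 60/76/87/94% overall and 50/66/79/89% for tacrolimus at 5/6/7/8 points. The tacrolimus comparison becomes primary if the CNI interaction is significant.

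**Working it through.** **Inputs from the documents.** 1020 per arm (816 tacrolimus, 80%); 50% control rate; one-sided 0.025; 10% margin; at least 50% living donors.

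**Assumptions, not in the documents.** Donor mix LD/SCD/ECD of 50/35/15 or 50/25/25. Control event rates: A 45/52/60%, B 40/52/75%, C 35/55/85%. The same risk difference d in every stratum, complete data, exact balance within strata.

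**The plan's own figures.** The unstratified two-proportion test with continuity correction gives 60.1/76.2/87.9/94.8% for the overall FAS at 5/6/7/8 points (stated 60/76/87/94). Without the correction it gives 61.9/77.5/88.7/95.3%. Non-inferiority power is Φ(0.10/√(0.5/1020) − 1.96) = 99.5% (stated >99). Table 9-1 is therefore reproduced to within 2 points.

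**Formulas.** With stratum weights w, N per arm, and control and everolimus rates pC and pE:
- Crude variance: Vc = [p̄C(1−p̄C) + p̄E(1−p̄E)]/N, from overall rates.
- Within-stratum variance: Vw = Σ w[pC(1−pC) + pE(1−pE)]/N. This is the true variance of either estimate under stratified randomisation.
- Crude power = Φ((d − 1.96√Vc)/√Vw); stratified power = Φ(d/√Vw − 1.96).
- Actual one-sided error of the crude test = Φ(−1.96√(Vc/Vw)).

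**One case in full: B, mix 50/35/15, d = 0.06, N = 1020.**
- p̄C = 0.5×0.40 + 0.35×0.52 + 0.15×0.75 = 0.4945; p̄E = 0.4345.
- Vc = (0.24997 + 0.24571)/1020, so SE = 0.02204.
- Vw = (0.5×0.4644 + 0.35×0.4980 + 0.15×0.4014)/1020 = 0.46671/1020, so SE = 0.02139. The variance is 5.8% smaller.
- Crude power = Φ((0.06 − 0.0432)/0.02139) = 78.4%. Stratified power = Φ(2.805 − 1.96) = 80.1%.
- With no difference, NVc = 0.49994 and NVw = 0.47097, so the crude error is Φ(−1.96×1.0303) = 0.022.

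**All cases** (ranges are over the two mixes):

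| | Equal rates | A | B | C |
|---|---|---|---|---|
| Variance reduction | 0 | 1–2% | 6–8% | 12–17% |
| Crude one-sided error | 0.025 | 0.024 | 0.020–0.022 | 0.016–0.018 |
| CI half-width, crude → stratified (points) | 4.3 → 4.3 | 4.3 → 4.3 | 4.3 → 4.2 | 4.3 → 4.0–4.1 |
| Overall power at 6 points, crude (%) | 77.6 | 77.8 | 78.4–78.5 | 79.2–79.6 |
| Overall power at 6 points, stratified (%) | 77.6 | 78.1–78.2 | 80.1–80.9 | 82.8–84.5 |
| Overall gain at 5 points | 0 | 0.4–0.6 | 2.2–3.2 | 4.9–6.9 |
| Overall gain at 7 points | 0 | 0.2–0.3 | 1.0–1.5 | 2.1–2.8 |
| Overall gain at 8 points | 0 | 0.1 | 0.5–0.7 | 0.9–1.2 |
| Tacrolimus power at 6 points, crude (%) | 68.2 | 68.3 | 68.8 | 69.4–69.6 |
| Tacrolimus power at 6 points, stratified (%) | 68.2 | 68.7–68.8 | 70.8–71.7 | 73.9–75.9 |
| Tacrolimus gain at 7 points | 0 | 0.3–0.4 | 1.5–2.2 | 3.2–4.3 |

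Non-inferiority power rises by at most about 0.1 point overall and 0.4 for tacrolimus. In a separate calculation with similar donor-type spreads, adding a 10-point difference between the CNIs changed stratified power by at most 0.3 points.

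**Simulation** (200,000 trials per scenario, six balanced strata, 1020 per arm). Crude error was 0.023–0.024 (A), 0.020–0.021 (B) and 0.015–0.018 (C). Stratified error was 0.025–0.027. Power at 6 points, crude against stratified: A 77.3 against 78.5–78.6%; B 78.0 against 80.4–80.9%; C 78.7–79.0 against 82.8–84.6%.

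**The case against.** The plan contains no error here. The crude interval is valid, the type I error is at or below its nominal level, and Table 9-1 powers the same unstratified test that is run. A simple conservative risk difference is a legitimate choice. The gain depends on event rates that the documents do not give; the larger figures need a spread such as 35% against 85%, which no section supports. At the 7-point difference the sample-size text singles out, the overall gain is 0.2 to 2.8 points, and superiority is only the third step of the hierarchy. The strata are not ignored either: the endpoint is analysed by donor type and by CNI, and a significant interaction leads to testing within CNI.

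All of this is correct and limits the point to efficiency. Two further cautions also stand. The simulated stratified error runs slightly above 0.025, so part of the simulated gain, most visibly in A, is a small-sample effect. In a 400,000-trial check the error was 0.0252–0.0263 with the plug-in SE and 0.0250–0.0259 with the Sato SE, so the SE should be named. Changing the primary method late in an open-label trial would also look data-driven.

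The objection does not show a reason to leave the strata out of the decisive test. Subgroup results and the interaction model do not supply a stratified overall difference, and testing within CNI still leaves donor type out.

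**Conclusion.** The concern holds, as a loss of efficiency and not a validity error. The primary interval is unstratified although the design is stratified. Under the assumed rates and mixes, with complete data and exact balance within strata, the overall superiority power forgone at 6 points runs from 0.3 to 4.9 percentage points, and for tacrolimus alone from 0.4 to 6.3. It is zero if strata have equal rates. Multiple imputation would alter the SEs slightly but not the direction. Non-inferiority conclusions and the stated sample size are unaffected.

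**What to change.** In each imputed dataset, estimate the Mantel-Haenszel risk difference for event = 1 over the six donor-type-by-CNI strata, with a named SE (the Sato variance is suitable). Combine by Rubin's rules and use that interval for both the 10% margin and superiority. With 1:1 allocation within strata, the weights follow stratum size, so the target is still the overall difference in H01 and H03. If the interaction test leads to separate analyses, stratify by donor type only within each CNI.

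State which strata are used. The balance holds for the strata entered in the IRT, which suit the primary test, with actual initial strata as a sensitivity analysis. The current text points the other way: SAP 2.2 analyses patients "according to their randomized treatment assignment and according to the actual stratum they initially belong to", and SAP 2.2.1 adds for subgroups that "donor type will be derived based on Kidney Donor Background Information eCRF, and not the randomization stratification from IRT". Align the SAP 2.2 wording, and the matching sentence in Protocol 9.1, with the choice made.

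In SAP 4.7.1, feed the common risk difference and its SE to the third PROC MIANALYZE step. Keep the existing output for the crude arm rates, and report the crude difference as a sensitivity result.

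The cost is amended wording in Protocol 9.4.2.2 and SAP 2.5.2.1, one PROC FREQ request, one PROC MIANALYZE input and one table. The smallest stratum would hold about 1020 × 0.15 × 0.20 ≈ 31 patients per arm under the 50/35/15 mix, enough for Mantel-Haenszel.

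The change must be fixed before Month 12 results are known. Last first treatment was January 2016 and this SAP is dated February 2018. If those results are already known, add the stratified difference only as a labelled sensitivity analysis.
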